### 6.7.3. Dose-limiting Toxicity Guidelines

A DLT will be defined as any event at least possibly related to ELI-002 as follows:

- a. Any Grade  $\geq 3$  non-hematologic toxicity except asymptomatic laboratory abnormalities (see Section 12.2.1.1)
- b. Any Grade  $\geq 3$  toxicity involving major organ systems for greater than 72 hours and occurring within 28 days of subcutaneous administration
- c. Grade 3 CRS that does not resolve to  $\leq$  Grade 2 within 7 days
- d. Any Grade 4 CRS that does not improve to  $<$  Grade 2 within 72 hours
- e. Any Grade  $\geq 3$  autoimmune disorder
- f. Any Grade  $\geq 3$  rash that does not resolve to  $\leq$  Grade 1 within 7 days with appropriate treatment

The DLT observation period will be 28 days.

Maximum tolerated dose definition: The MTD is defined as the highest dose level with a DLT incidence  $<33\%$  of cohort subjects.

See protocol Section 6.7.1 and Section 6.8 for management of toxicity.

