## 1. SYNOPSIS

Name of Sponsor/Company: Elicio Therapeutics, Inc. (hereafter, referred to as Elicio)		
Name of Investigational Product: ELI-002		

Name of Active Ingredient: ELI-002 is an 8-component product consisting of: up to 7 lipid-conjugated peptide-based antigens (amphiphilic peptides, referred to as ‘Amph-Peptides’) and a lipid-conjugated immune-stimulatory oligonucleotide (‘Amph-CpG-7909’) dosed after an admixing procedure of the respective Amph-Peptide and Amph-CpG-7909 drug products.
 
During the Phase 1 (dose escalation) study, the Amph-Peptide mixture (Amph-Peptides 2P) will be comprised of 1.4 mg of 2 Amph modified KRAS peptides, Amph-G12D, and Amph-G12R (0.7 mg/peptide). Elicio plans to investigate the use of an Amph-Peptide 7P drug product containing all 7 Amph-Peptides (G12D, G12R, G12V, G12A, G12C, G12S, G13D) in future clinical trials.
		
Protocol Number: ELI-002-001	Phase: 1	Country: United States (of America)
Title of Trial: First in Human Phase 1 Trial of ELI-002 Immunotherapy as Treatment for Subjects with Kirsten Rat Sarcoma (KRAS) Mutated Pancreatic Ductal Adenocarcinoma (PDAC) and Other Solid Tumors		
Trial centers: Multicenter		
Investigators: Multicenter		

Studied period (years):
 
Date first subject enrolled: 4Q2021
 
Date last subject enrolled: 2Q2023
		

Hypothesis:
 
ELI-002 is safe and the maximum tolerated dose (MTD) and/or recommended Phase 2 dose (RP2D) can be established at the end of the Phase 1 dose escalation.
		

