The RP2D will be defined in consideration of the MTD (if any), safety data, and pharmacodynamic data. The RP2D will be communicated to all sites in a trial memo following the last SMC cohort review.

Subject replacement: If a subject discontinues for any reason other than toxicity prior to completing 28 days of ELI-002 therapy, a replacement subject will be added to the cohort until 3 subjects per cohort complete 28 days of ELI-002 therapy.

DLT definition: A DLT will be defined as any event at least possibly related to ELI-002 as follows:

- a. Any Grade  $\geq 3$  non-hematologic toxicity except asymptomatic laboratory abnormalities (see Section 12.2.1.1)
- b. Any Grade  $\geq 3$  toxicity involving major organ systems for greater than 72 hours and occurring within 28 days of subcutaneous administration
- c. Grade 3 CRS that does not resolve to  $\leq$  Grade 2 within 7 days
- d. Any Grade 4 CRS that does not improve to  $<$  Grade 2 within 72 hours
- e. Any Grade  $\geq 3$  autoimmune disorder
- f. Any Grade  $\geq 3$  rash that does not resolve to  $\leq$  Grade 1 within 7 days with appropriate treatment

The DLT observation period will be 28 days.

MTD definition: The MTD is defined as the highest dose level with a DLT incidence  $<33\%$  of cohort subjects.

The trial will consist of a Screening Period, an Immunization Period, a No Dosing 3-Month Period, a Booster Period, and a Follow-up Period.

A Booster Period is provided as further lymph node antigen exposure may be required to maintain effective levels of antigen-specific T-cells. All subjects will receive booster doses unless they have unresolved toxicity.

All subjects will be observed for safety and tolerability. CT imaging with contrast will occur at screening and 35 days post first dose and at additional timepoints until radiographic relapse is observed.

The central laboratory will confirm  $\geq 1$  of 2 mutant KRAS/NRAS alleles targeted by ELI-002 Amph-Peptides 2P (G12D, and G12R,) is present and central laboratory ctDNA must be positive or there must be serum tumor biomarker (such as CA19-9, CEA, and CA-125) elevation at  $\geq 21$  days post-surgery or after last administration of adjuvant therapy (whichever comes last in the specific subject treatment plan). These data are required for determination of eligibility and inclusion into the trial.

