In any cohort, if none of the subjects experience a DLT during the first 28 days following first administration of ELI-002, the dose escalation will occur, and 3 subjects will be enrolled in the cohort at the next dose level. However, if 1 of the 3 or 4 initial subjects in a cohort experiences a DLT, then 3 (or 2, if 4 were originally enrolled) additional subjects will be enrolled at the same dose level. If 2 or more of 3 subjects within a cohort experience a DLT, then this dose will be considered the toxic dose. If only 1 of 6 subjects within a cohort experiences a DLT during the first 28 days of treatment, then the next cohort may begin enrollment. If 2 or more of 6 subjects within a cohort experience a DLT during the first 28 days, then this dose will be considered the toxic dose. The trial may proceed at a lower dose, at a less frequent schedule, or omitting the Amph-CpG-7909 adjuvant while continuing to administer the Amph-Peptides, based on emerging toxicity or pharmacodynamic data until the MTD is determined.

A trial memo will be sent to all sites following each SMC meeting summarizing the decision; if additional cohorts are to be enrolled, the dose level and schedule will be provided.

Safety monitoring is further detailed in the SMC Charter.

The RP2D will be defined in consideration of the MTD (if any), safety data, and pharmacodynamic data. The RP2D will be communicated to all sites in a trial memo following the last SMC cohort review. Once the RP2D is determined, the cohort evaluating the Phase 2 dose will be expanded as needed so that there is safety experience with at least 6 subjects at this dose level.

Please refer to [Section 6.7](#) for management of study drug-related events. DLT Guidelines are specifically detailed in [Section 6.7.3](#).

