### **6.1.5.2. Applying the IVD Results in the Clinical Trial**

ELI-002-001 is a Phase 1, open-label trial of ELI-002 as adjuvant therapy for subjects with mKRAS/mNRAS+ solid tumors who have no standard available treatment. These subjects have undergone surgical resection and may have positive MRD as determined by detectable ctDNA. MRD will be defined as the presence of ctDNA in the subject's body, in which the primary tumor has been removed and the subject is currently without clinical signs of disease. The mKRAS/mNRAS+ status will be confirmed by CGP WES from tumor samples versus normal germline or from plasma RAS ctDNA from plasma samples, and ctDNA status will be determined by either the tumor-informed or plasma RAS ctDNA assays at screening.

Approximately 18 subjects are planned to be treated in 3 planned dose level cohorts. The RP2D will be determined by consideration of the MTD (if any MTD is observed), safety data, and pharmacodynamic data.

Baseline mKRAS/mNRAS status and ctDNA status for eligibility will be assessed during screening.

The tumor-informed personalized ctDNA or plasma RAS ctDNA assays to detect mKRAS/mNRAS and MRD status will be used to assess subject eligibility for enrollment.

The prevalence of mutations in KRAS and NRAS to be evaluated by the IVDs is reviewed in detail in protocol [Section 4.1](#). The prevalence of NRAS mutations is highest in CRC among tumor types included in this study, while KRAS mutations are found across all histologies.

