## **6.2. Endpoints**

### **6.2.1. Primary Endpoints**

The primary endpoints of Phase 1 are:

- To define the MTD of ELI-002 (in the event there is an MTD) and the RP2D
- To evaluate safety as assessed by the incidence of AEs and clinically significant in laboratory tests and vital signs

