### **MTD definition:**

The MTD is defined as the highest dose level with a DLT incidence  $<33\%$  of cohort subjects.

[figure not shown]
A trial memo will be sent to all sites following each SMC meeting summarizing the decision; if additional cohorts are to be enrolled, the dose level and schedule will be provided.

Safety monitoring is further detailed in the SMC Charter.

The RP2D will be defined in consideration of the MTD (if any), safety data, and pharmacodynamic data. The RP2D will be communicated to all sites in a trial memo following the last SMC cohort review. Once the RP2D is determined, the cohort evaluating the Phase 2 dose will be expanded as needed so that there is safety experience with at least 6 subjects at this dose level.

The Study Flow Chart is presented in Figure 1.

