## 9.0 STUDY ENDPOINTS

### 9.1 Endpoints

#### 9.1.1 Phase 1 Primary Endpoints

- To define the MTD of ELI-002 (in the event there is an MTD) and the recommended Phase 2 dose (RP2D)
- To evaluate safety as assessed by the incidence of adverse events (AEs) and clinically significant changes in laboratory tests and vital signs

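### The MTD definition needs no toxic dose above it, so if every tested level has under 33% DLTs, the last dose tested is reported as the MTD

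*Protocol*

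**What the plan says.** The definition appears three times with the same content. Protocol 6.7.3 has "Maximum tolerated dose definition: The MTD is defined as the highest dose level with a DLT incidence" below 33% of cohort subjects, the Protocol synopsis has the same rule, and SAP 8.1 repeats it ("The MTD is defined as the highest dose level with a DLT incidence", again below 33%). No further condition is attached.

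Other parts of the plan treat the MTD as something that may not exist:

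- The synopsis hypothesis is that "the maximum tolerated dose (MTD) and/or recommended Phase 2 dose (RP2D) can be established at the end of the Phase 1 dose escalation".
- The primary endpoint in Protocol 6.2.1 is "To define the MTD of ELI-002 (in the event there is an MTD) and the RP2D", and SAP 9.1.1 carries the same proviso.
- Protocol 6.1.5.2 states "The RP2D will be determined by consideration of the MTD (if any MTD is observed), safety data, and pharmacodynamic data". Protocol 6.1.1 and SAP 8.1 make the RP2D depend on the MTD in similarly conditional terms.

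The escalation text has its own toxicity label. In Protocol 6.1.1, "If 2 or more of 3 subjects within a cohort experience a DLT, then this dose will be considered the toxic dose", and the same holds for 2 or more of 6. The MTD definition does not refer to this label. After a toxic dose, the trial may go on with a lower dose, a less frequent schedule or no adjuvant until an MTD is found.

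The Protocol plans three adjuvant levels (0.1, 0.5 and 2.5 mg). The SAP lists two more (5.0 and 10.0 mg). SAP section 14, which records departures from the protocol analysis, says nothing on the MTD.

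**The concern.** A maximum tolerated dose implies that something above it was not tolerated. The written rule drops that half of the idea. If every level passes, the label goes to whichever dose was tried last, so it marks where testing stopped and not where tolerance ended. Adding the 5.0 and 10.0 mg cohorts would simply move the label up.

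The definition and the endpoint then disagree. The endpoint foresees that no MTD may emerge, but no section says when that is so or what to report instead. Two analysts with the same data could report different results for a primary endpoint: one an MTD equal to the top dose, the other no MTD.

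**Working it through.** **1. Which cohort results meet the rule.** The cut-off is below 33%.

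- Below 33%: 0/3, 0/4, 0/5 and 0/6 (0%), 1/6 (16.7%), 1/5 (20%) and 1/4 (25%, although 1/4 must expand).
- Not below 33%: 1/3 and 2/6 (both 33.3%), 2/5 (40%), 2/4 (50%), 2/3 (66.7%) and above.

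Every result that the 3+3 text lets through (0/3, 0/6, 1/6) therefore meets the MTD criterion. If all levels are let through, the highest level meeting the criterion is the top dose tested: 2.5 mg with three levels, 10.0 mg with five. Read literally, there is no MTD only when no tested level is below 33%, that is, when even the lowest dose fails and no lower or modified regimen passes.

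**2. How often every level passes.** The documents give no DLT rates, so the rates below are assumptions. With DLT rate p and q = 1 − p, a level clears 3+3 on 0/3, or on 1/3 followed by 0/3:

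P(clear) = q³ + 3pq² × q³ = q³ + 3pq⁵

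This gives 0.9734 (p = 0.05), 0.9061 (0.10), 0.7086 (0.20), 0.4943 (0.30), 0.3093 (0.40) and 0.1719 (0.50). Multiplying over levels, for example 0.9061 × 0.7086 × 0.4943 = 0.317:

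| Assumed DLT rates | Levels | 3+3 | Six per cohort from the start, at most 1 DLT |
|---|---|---|---|
| flat 5% | 3 | 0.922 | 0.905 |
| flat 10% | 3 | 0.744 | 0.695 |
| 10/20/30% | 3 | 0.317 | 0.244 |
| 30/40/50% | 3 | 0.026 | 0.011 |
| flat 5% | 5 | 0.874 | 0.847 |
| flat 10% | 5 | 0.611 | 0.545 |
| 10/20/30/40/50% | 5 | 0.017 | 0.006 |

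The lowest level itself fails 3+3 with probability 1 − P(clear): 0.027, 0.094 and 0.506 at 5%, 10% and 30%. That is the one situation in which the definition and the conditional endpoint can agree that there is no MTD.

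**3. Does the optional Full Analysis Set analysis change?** Protocol 13.2.2.1 and SAP 11.1 refer to subjects treated at the MTD and at lower doses. When every level passes, the current rule sets that reference at the top dose tested. If the MTD is reported as not reached and the reference becomes the highest dose level tested, the dose and the subjects are the same. The effect is nil.

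**4. Does the proposed criterion cover every final cohort result?** Cohorts of 3 to 6 have 4 + 5 + 6 + 7 = 22 possible counts. Removing 1/3 and 1/4, which must expand, leaves 20. Six are below 33% (0/3, 0/4, 0/5, 1/5, 0/6, 1/6). Seven are declared toxic by the 3+3 text (2/3, 3/3, 2/6 to 6/6). Seven are at or above 33% but not named there (2/4 to 4/4, 2/5 to 5/5). A criterion of 33% or more in a completed cohort, or declared toxic, sorts all 20.

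At trial level there is one further case: the lowest level is toxic and a modified schedule at that same dose passes. No dose level then lies below the toxic one, so the definition must admit modified regimens.

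**The case against.** The strongest reply is that the texts can be read together. The endpoint is conditional, the RP2D text is conditional, and the sentence after the toxic-dose rule places the finding of an MTD after a toxic dose. This is good evidence of intent. It is not a rule: none of these statements overrides the definition or says what to report when every level passes.

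It is also said that only a label is at issue. That stands. Escalation has its own rules. Protocol 4.6.5 has the safety committee weigh all safety observations, and the planned adverse event summaries in SAP 13.7.1 would show DLTs by cohort beside the label. A reader might infer that the definition could push the RP2D upward or change who enters the Full Analysis Set analyses. The documents support neither: the RP2D also rests on safety and pharmacodynamic data, and the subjects are the same either way.

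The probabilities rest wholly on assumed rates and measure how often the label would apply, not harm. That is correct. The exact 95% intervals for a top cohort at 0/6 (0 to 46%) or 1/6 (0.4 to 64%) do not help either. They would be the same for an MTD with a toxic dose above it, so they do not separate the two definitions.

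The SMC Charter and the table templates are not among the documents and might settle the matter. If so, the SAP should match them; it cannot rely on them unseen.

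**Conclusion.** The point holds and should be corrected. It is a stated rule that gives a wrong conclusion in a foreseeable case, and it concerns a primary endpoint. The logic needs no assumption about DLT rates. The frequency does: for three planned levels under 3+3, the case arises in 92% of trials at a flat 5% and in 3% at 30/40/50%.

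The consequence is limited to the reported MTD conclusion. No dose, escalation step, sample size, RP2D decision or analysis population changes. A reader might also infer that this trial has reported, or will report, a false MTD. The documents contain no DLT counts, so they do not show whether every tested level passed.

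**What to change.** Define the MTD as the highest dose level, or modified regimen, with DLT incidence below 33% for which a higher or more intensive tested level either had DLT incidence of 33% or more in its completed cohort or was declared the toxic dose. A cohort at 1/3 or 1/4 that awaits its required expansion is not complete. Add two reporting outcomes:

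- If no tested level meets the toxicity criterion, report 'MTD not reached', with the highest dose level tested and its DLT n/N.
- If the lowest level meets it and no lower or modified regimen passes, report 'no MTD identified'.

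The wording belongs in the Protocol synopsis, Protocol 6.7.3 and SAP 8.1. For consistency only, the Full Analysis Set text (Protocol 13.2.2.1 and SAP 11.1) should refer to the highest dose level tested when no MTD is reached.

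Planned enrolment was to end in 2Q2023 and the SAP is for the final analysis. At this stage it is enough to make the change in SAP 8.1, with the clause in SAP 11.1, and to record it in SAP section 14. No protocol amendment is needed. The cost is a short paragraph and one clause. The downside is that the primary endpoint may read 'MTD not reached'.

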## 6.8. Management of Risks and Toxicities

Review of the ELI-002 pre-clinical data indicates that certain cytokine levels such as IL-6 may be elevated (see Section 4.4). Elevated cytokines are a hallmark of CAR-T cell therapies often leading to CRS and ICANS which can be serious or fatal.

Consequently, the management of such toxicities have been extensively reviewed through the CAR-T Toxicity Management Workgroup [Lee et al, 2019]. To be fully prepared in the event that CRS is observed, this trial will follow the same guidelines as are used for CAR-T studies as outlined in Section 6.8.1 through Section 6.8.2.

All subjects will be monitored for potential AEs such as CRS. In addition, there will be a 1-week stagger between enrollment of the first subject in a cohort and the subsequent subjects. In addition, all patients will be asked to stay within one hour travel time to the clinic for at least 24 hours following their first ELI-002 dose.

### 6.8.1. Management of Cytokine Release Syndrome

Since ELI-002 activates T cells by a novel amphiphile mechanism whereby potent responses are generated, there is a theoretical risk for observation of T-cell-mediated toxicity.

To reduce the risk of CRS, subjects will not be given a repeat dose of ELI-002 if they are exhibiting  $T > 38^{\circ}\text{C}$  and/or  $\text{IL-6} > 500 \text{ pg/mL}$ . In addition, if a subject exhibits  $\text{IFN}\gamma \geq 1000 \text{ pg/mL}$ , the Elicio medical monitor should be contacted for consultation.

In the event the ELI-002 dose is held, the subject should not receive any make up dose and remain on the original protocol schedule (ie, their next dose will be at the next protocol-specified dose if they meet the criteria for dosing and with approval from the medical monitor).

Cytokine release syndrome is caused by the release of inflammatory cytokines such as IL-6, IL-2,  $\text{IFN}\gamma$ , and  $\text{TNF}\alpha$ , which causes a systemic inflammatory response similar to sepsis. The release of cytokines occurs when cells that are targeted by antibodies, immune effector cells (T and B-cells, Natural Killer cells, and monocytes/macrophages) are recruited to the tumor area and the subject's immune cells are activated. The importance of cytokine secretion of CAR T cells after exposure to tumor cells is closely related to their killing activity, and the degree of cytokine elevation is correlated to the bulk of residual disease at the time of adoptive T-cell infusion, ie, tumor burden, as well as with the number of detectable CAR T-cells after administration [Brentjens, 2012; Lee et al, 2015, Lee et al, 2019]. IL-6 levels in patients with low grade 0-3 CRS were a median of 100 pg/mL, whereas IL-6 was a median of 10,000 pg/mL [Teachey et al, 2016] in patients with high grade 4-5 CRS. Likewise,  $\text{IFN}\gamma$  was approximately 40 pg/mL in patients with low grade CRS, versus approximately 4,000 pg/mL in those with high grade CRS [Teachey et al, 2016]; therefore, this protocol takes a conservative cut-point and mandates dose hold for ELI-002 if  $\text{IL-6} > 500 \text{ pg/mL}$  is observed or contact with the medical monitor in the event that  $\text{IFN}\gamma > 1000 \text{ pg/mL}$  is observed, making the assumption that although CRS guidelines address CAR-T safety management, ELI-002 may elicit sufficient T cells to merit a similar approach. The goal of CRS management is to prevent life-threatening complications while preserving the antitumor T cell immune response.

Clinical signs and symptoms of CRS listed in [Table 17](#) should raise concern.

**Table 17: Clinical Symptoms of Cytokine Release Syndrome**

System	Symptom
Constitutional	Fever ± rigors, malaise, fatigue, anorexia, myalgias, arthralgias
Biochemical	Evidence of disseminated intravascular coagulation and MAS, elevation in liver function tests, D-dimers, LDH, CRP, uric acid and phosphorus
Skin	Rash
Gastrointestinal	Nausea, vomiting, diarrhea
Respiratory	Tachypnoea, hypoxaemia
Cardiovascular	Tachycardia, widened pulse pressure, hypotension, arrhythmias, increased cardiac output (early), potentially diminished cardiac output (late)
Coagulation	Disseminated intravascular coagulation, elevated D-dimer, hypofibrinogenaemia ± bleeding
Renal	Azotaemia
Hepatic	Transaminitis, hyperbilirubinaemia
Neurological	Headache, mental status changes, confusion, delirium, word-finding difficulty or frank aphasia, hallucinations, tremor, dysmetria, altered gait, seizures, cerebral edema

CRP=C-reactive protein; LDH=lactate dehydrogenase; MAS=macrophage activation syndrome

The Common Toxicity Criteria (ie, CTCAE) grading system was originally developed to capture a cytokine syndrome occurring during infusion therapy; therefore, it is inadequate to capture the delayed CRS that occurs after repeat dose ELI-002 administration. Appreciating the scale needed to be adapted for other therapeutics, to define mild, moderate, severe and life-threatening events, account for overlapping symptoms and guide treatment recommendations, and allow cross-trial comparison, an objective revised consensus CRS grading system was developed by the American Society for Transplantation and Cellular Therapy (ASTCT) as provided in [Table 18 \[Lee et al, 2019\]](#).

**Table 18: Suggested Treatment by Cytokine Release Syndrome Grade**

Grade	Treatment Requirement	Immunosuppressive Treatment
Grade 1	Symptoms are not life-threatening and require symptomatic treatment only (eg, fever, nausea, fatigue, headache, myalgias, malaise). Vigilant supportive care. Assess for infection, treat fever and neutropenia if present, monitor fluid balance	Acetaminophen and other antipyretics/analgesic supportive measures
Grade 2	Symptoms require and respond to moderate intervention : 
 
• Oxygen requirement <40%
 
• Vigilant Supportive Care
 
	Acetaminophen and other antipyretic/analgesic supportive measures. If multiple comorbidities or older age are present initiate IL-6 inhibition with tocilizumab ± corticosteroids
Grade 3	Symptoms require and respond to aggressive intervention : 
 
• Oxygen requirement ≥40% or
 
• Hypotension requiring at least one vasopressor
 
• Vigilant Supportive Care
 
	Initiate immunosuppressive therapy using tocilizumab and corticosteroids.
Grade 4	Life-threatening symptoms 
 
• Requirement for ventilator support or
 
• Grade 4 organ toxicity (excluding transaminitis)
 
	Initiate immunosuppressive therapy using tocilizumab and corticosteroids
Grade 5	Death	-

High-dose vasopressor doses shown in [Table 19](#).  
[[Lee et al, 2019](#)]

When applicable, use of high-dose vasopressor is recommended as described in [Table 19](#).

